3.1.6.1 Missing start and end dates for AE and concomitant medication (CM)

The assumption will be the worst or most conservative judgment when imputing AE and CM start and end dates. The purpose of imputing a start date is to help define whether the AE/CM started while taking study drug.

For a partial or missing start date:

- If the day is missing, the first day of the month will be imputed. If the missing day is the same as the month of first dose of study drug, then the first dose date will be imputed.
- If the day and month are missing, the first day of January will be imputed. If the year is the same as the first dose date, then the first dose date will be imputed.
- If the day is completely missing, the first dose date will be imputed. If the end date suggests it could have started prior to this, the first day of January of the same year as the end date will be imputed.
- When imputing a start date, the start date will ensure that the new imputed date is sensible, i.e., is prior to the end date of the AE or CM.

For a partial or missing end date:

- If the day is missing, the last day of the month or the last assessment date, whichever is earlier, will be imputed.
- If the day and month are missing, the 31st of December or the last assessment date, whichever is earlier, will be imputed

- If the date is completely missing, there will be a need to look at whether the AE/CM is still ongoing before imputing a date. If the ongoing flag is missing, then it will be assumed that AE is still present, or CM is still being taken (i.e., do not impute a date). If the AE/CM has stopped, then the last assessment date will be imputed.

These data imputations are for categorization purpose only and will not be used in the listings.

If the assessment of the relationship of the AE to tesevatinib is missing, then it will be assumed that the AE is related to tesevatinib and the AE considered as such in the frequency tables of possibly related AEs. No imputation should be done at the data level.

3.1.6.2 Missing event dates

Event date will be imputed only when day is missing, and the purpose of imputing an event date is to most conservatively calculate time to event.

If the day is missing, the first (mid, last) day of the month will be imputed for undesired (neutral, desired) event. If the missing day is the same as the month of first dose of study drug, then the first dose date will be imputed for undesired event.

These data imputations are for time to event calculation only and will not be used in the listings.

3.2 Analysis Populations

The following populations will be analyzed:

Modified Intent-to-treat (mITT) Population: The primary population for efficacy analyses will be a Modified Intent-to-treat (mITT) Population. For KD019-101 it is defined as all subjects who completed 28 days (for subjects in the Phase 2a portion of the study this will be 25 or 26 days in the Monday/Thursday and Monday/Wednesday/Friday cohorts, and 28 days in the 50 mg daily dosing cohort).

[REDACTED]

The mITT Population will be used for tables of demography, baseline characteristics, and efficacy.

Safety Population: The Safety Population is defined as all subjects who receive at least 1 dose of tesevatinib.

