10.3 Replacements

During the Phase 1b portion of the study, if any subject does not complete 28 days of treatment (excluding discontinuation or decrease in dose due to an AE), they will be replaced. A replacement subject will be obtained using the original eligibility criteria in the same dose cohort. Subjects discontinued from the Phase 2a portion of the study will not be replaced.

The maximum number of replacement subjects will be 6 subjects.

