14.3 Statistical Considerations

14.3.1 Study Populations

Adult subjects with ADPKD will be enrolled. The safety population will consist of all subjects who receive at least 1 dose of tesevatinib. An evaluable subject will be defined as one who has completed 28 days (for subjects in the Phase 2a portion of the study this will be 25 or 26 days in the Monday/Thursday and Monday/Wednesday/Friday cohorts, and 28 days in the 50 mg daily dosing cohort). Phase 1b unevaluable subjects (subjects who are not evaluable for toxicity) will be replaced. Subjects who do not complete the study, for whatever reason, will have all available data up until the time of termination related to the reason they were terminated included in the analysis. Completion of the study for subjects enrolled in the Phase 1b portion will be defined as uninterrupted completion of the first 28 days of study drug administration, and completion of the study for subjects entered in the Phase 2a portion of the study will be defined as completion of the Month 6 MRI.

For the Phase 2a cohort, all subjects treated will be included in the analyses based on their available data.

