3.7 Primary Endpoint Analysis

The primary endpoint for the Phase 1b portion of KD019-101 is safety and tolerability. This will be covered in Section 3.9.

The primary endpoint is annualized change in glomerular filtration rate (GFR) in subjects with ADPKD when treated with tesevatinib. The annualized change in GFR will be calculated as the percent change from baseline divided by total duration in days times 365.25.

This analysis will be done using the mITT population. Descriptive statistics will be provided for each cohort. The annualized GFR will be calculated for the 6, 12, 18 and 24 months timepoints.

GFR will be estimated using three equations; MDRD-4, CKD-EPI_{2012cys}, and CKD-EPI_{2012Scr-cys}.

4-Variable Modification of Diet in Renal Disease (MDRD-4) Equation

High Level Formula for Black or African-American Males:
$\text{Estimated GFR} = 175 \times (\text{Scr}^{-1.154}) \times (\text{Age}^{-0.203}) \times 1.212$
High Level Formula for Males NOT Black or African-American (any other option):
$\text{Estimated GFR} = 175 \times (\text{Scr}^{-1.154}) \times (\text{Age}^{-0.203})$
High Level Formula for Black or African-American Females:

Estimated GFR = $175 \times (\text{Scr}^{-1.154}) \times (\text{Age}^{-0.203}) \times 1.212 \times 0.742$
High Level Formula for Females NOT Black or African-American (any other option):
Estimated GFR = $175 \times (\text{Scr}^{-1.154}) \times (\text{Age}^{-0.203}) \times 0.742$

Note: Age is shown in years. Scr = serum creatinine

CKD-EPI_{2012cys} Equation to Predict Glomerular Filtration Rate (GFR)

Gender	Scys (mg/L)	Equation
Female	≤ 0.8	$133 \times (\text{Scys}/0.8)^{-0.499} \times 0.996^{\text{age}} (\times 0.932)$
	> 0.8	$133 \times (\text{Scys}/0.8)^{-1.328} \times 0.996^{\text{age}} (\times 0.932)$
Male	≤ 0.8	$133 \times (\text{Scys}/0.8)^{-0.499} \times 0.996^{\text{age}}$
	> 0.8	$133 \times (\text{Scys}/0.8)^{-1.328} \times 0.996^{\text{age}}$

Note: Age is shown in years. Scys= serum cystatin

CKD-EPI_{2012Scr-cys} Equation to Predict Glomerular Filtration Rate (GFR)

Gender	Scr (mg/L)	Scys (mg/L)	Equation
Female	≤ 0.7	≤ 0.8	$130 \times (\text{Scr}/0.7)^{-0.248} \times (\text{Scys}/0.8)^{-0.375} \times 0.995^{\text{age}} (\times 1.08, \text{ if black})$
		> 0.8	$130 \times (\text{Scr}/0.7)^{-0.248} \times (\text{Scys}/0.8)^{-0.711} \times 0.995^{\text{age}} (\times 1.08, \text{ if black})$

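### The SAP restricts Phase 2a efficacy and baseline tables to subjects who completed the first 25 to 28 days, although the protocol includes all treated Phase 2a subjects

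*SAP*

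**What the plan says.** SAP 3.2 defines a modified intent-to-treat population and makes it primary for efficacy: "For KD019-101 it is defined as all subjects who completed 28 days". For Phase 2a it adds that "this will be 25 or 26 days in the Monday/Thursday and Monday/Wednesday/Friday cohorts, and 28 days in the 50 mg daily dosing cohort". Its use goes beyond efficacy: "The mITT Population will be used for tables of demography, baseline characteristics, and efficacy". SAP 3.7 applies it to the primary GFR endpoint ("This analysis will be done using the mITT population"), and SAP 3.7.1.1 and 3.7.1.2 apply it to height-adjusted kidney volume and reciprocal creatinine. The post-hoc eGFR slope in SAP 3.7.2.1 names no population. The Safety Population is everyone with at least one dose.

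Protocol 14.3.1 contains almost the same 28-day wording, but for another purpose. There it defines who is evaluable: "An evaluable subject will be defined as one who has completed 28 days". That status drives replacement: "Phase 1b unevaluable subjects (subjects who are not evaluable for toxicity) will be replaced". The Phase 2a analysis rule is stated separately: "For the Phase 2a cohort, all subjects treated will be included in the analyses based on their available data". Protocol 10.3 adds: "Subjects discontinued from the Phase 2a portion of the study will not be replaced".

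**The concern.** The SAP appears to have taken the protocol's evaluability definition and used it as the efficacy set, under a name that suggests near-complete inclusion. Finishing the first four weeks is known only after dosing starts and is plausibly related to tolerability. Protocol 5.2.2.2.3 reports rash within 28 days in 4 of 9 subjects at 50 mg daily, 1 of 8 at 100 mg and 5 of 5 at 150 mg.

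Three things are at stake:

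- The reported Phase 2a set would not be the one the protocol specified.
- The baseline tables would describe a different group from the adverse-event tables.
- Any efficacy measure to which an early leaver could contribute would exclude that subject by rule.

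**Working it through.** **1. The two rules side by side (Phase 2a).**

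| Subject | Protocol 14.3.1 | SAP 3.2 |
|---|---|---|
| Treated, completes 25/26/28 days | included | included |
| Treated, leaves earlier | included, on available data | excluded from efficacy, demography and baseline |

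The second row is a direct conflict. The SAP lists no all-treated efficacy analysis. It also does not say 28 days of what. Protocol 11.3 permits drug to be held during the first 28 days except in Phase 1b, so a Phase 2a subject with an early interruption could be classified either way.

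**2. Which outputs can change.**

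- *GFR at Months 6, 12, 18 and 24, and six-monthly kidney volume:* little. A subject who leaves before Day 28 would rarely have a value at those times, and SAP 3.1.6 does not impute.
- *Demography and baseline:* every excluded subject drops out of these tables but stays in the safety tables.
- *Reciprocal creatinine:* SAP 3.7.1.2 uses each subject's first and last timepoint with no minimum follow-up. Early leavers can have a last value, because Protocol 10.1 and 9.7 call for End-of-Study laboratory tests 30 days after the last dose.
- *eGFR slope:* indeterminate, since no population is named.

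**3. Precision.** The plan's own figure reproduces. Half-width of the 80% interval with n = 65 and SD = 4.0 (SAP 3.1.2):

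1.2816 × 4.0 / √65 = 0.636 (0.642 with t on 64 df), against 0.64 stated.

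The documents give no early-exit rate. Under assumed exclusions:

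| Excluded (assumed) | n | Half-width (z) |
|---|---|---|
| 0% | 65 | 0.636 |
| 5% | 62 | 0.651 |
| 10% | 58 | 0.673 |
| 20% | 52 | 0.711 |

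These overstate the cost of the definition, because most such subjects would have no Month 6 value under either rule.

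**4. What happens if early leavers are simply added to reciprocal creatinine.** The annualized percent change is (Cr_first / Cr_last − 1) × 365.25 / days. Protocol 5.2.2.2.3 gives median creatinine rises of 22% at Day 7 and 13% at Day 28 in the Phase 1b 50 mg cohort, and attributes the rise to blocked tubular secretion. For a subject at those medians whose last sample is on drug:

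- Day 7: (1/1.22 − 1) × 365.25/7 ≈ −941% per year
- Day 28: (1/1.13 − 1) × 365.25/28 ≈ −150% per year

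In an unweighted mean of 65 with the other 64 at zero (an assumption), one such subject moves the mean by −941/65 ≈ −14.5 or −150/65 ≈ −2.3 percentage points per year. The Day 28 subject already counts as a completer, so the restriction does not cure this.

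With weighting by follow-up, the Day 7 subject has weight 7/(7 + 64 × 183) = 0.0006 if the others have about 6 months, or 7/(7 + 64 × 730) = 0.00015 if they have about 24. The shift falls to about −0.56 or −0.14 points.

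**The case against.** The strongest defence is that the restriction does little harm. The primary endpoint sits at Months 6 to 24. The study is open-label and nonrandomized with descriptive efficacy summaries. Early leavers stay in the Safety Population, discontinuations are summarized with reasons, and a listing of patients excluded from efficacy is planned. That stands, and it limits the size of the point. It does not explain the departure from the protocol or justify removing dosed subjects from demography.

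A second defence is that the cut-off keeps distorted short-follow-up values out of reciprocal creatinine. The distortion is real, although an off-drug End-of-Study sample would lessen it. The remedy belongs in the estimator, because a subject whose last value is at Day 28 passes the filter with a similar problem.

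Stronger readings are tempting but unsupported:

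- *That 60% of a cohort vanishes.* Three of 5 subjects at 150 mg daily withdrew, mainly over rash. But that cohort is Phase 1b, where the protocol itself uses 28-day evaluability and replacement, and the withdrawals are not dated.
- *That several 50 mg subjects are lost.* No early-exit rate is given. Day 28 creatinine changes are reported from all 9 Phase 1b 50 mg subjects, so zero is plausible.
- *That the GFR result is biased towards those who tolerate the drug.* Nothing in the documents links intolerance to GFR decline, and the excluded subjects would seldom have had a Month 6 value.

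**Conclusion.** Wrong as written: the SAP contradicts the protocol's stated Phase 2a analysis set and gives no reason. The practical effect falls on demography and baseline and on first-to-last reciprocal creatinine. The eGFR slope is unclear for want of a named population. Fixed-timepoint GFR and kidney volume would change little.

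The number excluded cannot be derived from the documents, and zero at 50 mg is within the range. The precision and annualization figures are illustrations that rest on the stated assumptions; they do not estimate what will occur. The conclusion needs none of them, since it follows from the two texts.

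**What to change.** - For Phase 2a, define the primary efficacy set as all treated subjects with available data, as in Protocol 14.3.1.
- Use the Safety Population for demography and baseline.
- Keep the 25-, 26- or 28-day completers as a sensitivity set labelled evaluable. State whether the days refer to treatment or follow-up, and report exclusions by cohort and reason.
- Name the population for the eGFR slope.
- For reciprocal creatinine and eGFR slope, replace the unweighted mean of annualized first-to-last values with a mixed-model slope, or weight by follow-up, so that early leavers are included without dominating the mean. This change should accompany the population change. It deals with short follow-up; the early secretion-related creatinine rise is a separate matter for interpretation.

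The population changes are SAP wording. The slope model and the sensitivity tables add a small amount of analysis work. No additional data collection is needed. If the sponsor prefers the restriction, the SAP should state and justify the departure from the protocol.

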3.3 Subject Disposition and Evaluability

Subjects who failed screening (i.e., subjects who signed the informed consent were screened but never started the study treatment, and their basic demographics and any AE after signing the informed consent may have been collected in the CRF) will be excluded from any populations defined in [Section 3.2](#). Therefore, these subjects will be excluded from any summary tables or listings.

The number of subjects discontinuing from the study and the primary reason for discontinuation will be summarized.

3.4 Protocol Deviations

All protocol deviations will be identified and classified as major or minor before clinical database lock and all major protocol deviations will be presented in a listing.

Major Deviation: Protocol deviation that may impact the accuracy, and/or reliability of the study data or that may impact subject rights, safety or well-being.

Minor Deviation: Protocol deviation that does not impact the accuracy, and/or reliability of the study data or subject rights, safety or well-being.

3.5 Demographics and Baseline Characteristics

3.5.1 Demographics

Subject demographics and baseline characteristics will be summarized for the mITT Population by cohort and study. Descriptive statistics will be provided for age, height, and weight.

3.5.2 Medical History

Medical history will be summarized by primary System Organ Class (SOC) and Preferred Term (PT). Medical history will be coded using Medical Dictionary for Regulatory Activities (MedDRA) Version 18.1 (or higher) terminology.

3.6 Prior and Concomitant Medications

Concomitant medications will be coded using the World Health Organization Drug Dictionary. Prior medications are defined as those medications that began and stopped before the start of study treatment. Concomitant medications are defined as medications taken after the start of study treatment and during the study period, including those began before but ongoing at the start of study treatment. If a medication start date is partially or fully missing and it is unclear as to whether the medication is prior or concomitant, it will be assumed that the medication is concomitant.

Number and percentage of incidence of prior and CM will be summarized according to study, cohort, Anatomical Therapeutic Class (ATC) and preferred drug name.

3.7 Primary Endpoint Analysis

The primary endpoint for the Phase 1b portion of KD019-101 is safety and tolerability. This will be covered in Section 3.9.

The primary endpoint is annualized change in glomerular filtration rate (GFR) in subjects with ADPKD when treated with tesevatinib. The annualized change in GFR will be calculated as the percent change from baseline divided by total duration in days times 365.25.

This analysis will be done using the mITT population. Descriptive statistics will be provided for each cohort. The annualized GFR will be calculated for the 6, 12, 18 and 24 months timepoints.

GFR will be estimated using three equations; MDRD-4, CKD-EPI_{2012cys}, and CKD-EPI_{2012Scr-cys}.

4-Variable Modification of Diet in Renal Disease (MDRD-4) Equation

High Level Formula for Black or African-American Males:
$\text{Estimated GFR} = 175 \times (\text{Scr}^{-1.154}) \times (\text{Age}^{-0.203}) \times 1.212$
High Level Formula for Males NOT Black or African-American (any other option):
$\text{Estimated GFR} = 175 \times (\text{Scr}^{-1.154}) \times (\text{Age}^{-0.203})$
High Level Formula for Black or African-American Females:

Estimated GFR = $175 \times (\text{Scr}^{-1.154}) \times (\text{Age}^{-0.203}) \times 1.212 \times 0.742$
High Level Formula for Females NOT Black or African-American (any other option):
Estimated GFR = $175 \times (\text{Scr}^{-1.154}) \times (\text{Age}^{-0.203}) \times 0.742$

Note: Age is shown in years. Scr = serum creatinine

CKD-EPI_{2012cys} Equation to Predict Glomerular Filtration Rate (GFR)

Gender	Scys (mg/L)	Equation
Female	≤ 0.8	$133 \times (\text{Scys}/0.8)^{-0.499} \times 0.996^{\text{age}} (\times 0.932)$
	> 0.8	$133 \times (\text{Scys}/0.8)^{-1.328} \times 0.996^{\text{age}} (\times 0.932)$
Male	≤ 0.8	$133 \times (\text{Scys}/0.8)^{-0.499} \times 0.996^{\text{age}}$
	> 0.8	$133 \times (\text{Scys}/0.8)^{-1.328} \times 0.996^{\text{age}}$

Note: Age is shown in years. Scys= serum cystatin

CKD-EPI_{2012Scr-cys} Equation to Predict Glomerular Filtration Rate (GFR)

Gender	Scr (mg/L)	Scys (mg/L)	Equation
Female	≤ 0.7	≤ 0.8	$130 \times (\text{Scr}/0.7)^{-0.248} \times (\text{Scys}/0.8)^{-0.375} \times 0.995^{\text{age}} (\times 1.08, \text{ if black})$
		> 0.8	$130 \times (\text{Scr}/0.7)^{-0.248} \times (\text{Scys}/0.8)^{-0.711} \times 0.995^{\text{age}} (\times 1.08, \text{ if black})$
	> 0.7	≤ 0.8	$130 \times (\text{Scr}/0.7)^{-0.601} \times (\text{Scys}/0.8)^{-0.375} \times 0.995^{\text{age}} (\times 1.08, \text{ if black})$
		> 0.8	$130 \times (\text{Scr}/0.7)^{-0.601} \times (\text{Scys}/0.8)^{-0.711} \times 0.995^{\text{age}} (\times 1.08, \text{ if black})$
Male	≤ 0.7	≤ 0.8	$130 \times (\text{Scr}/0.9)^{-0.207} \times (\text{Scys}/0.8)^{-0.375} \times 0.995^{\text{age}} (\times 1.08, \text{ if black})$
		> 0.8	$130 \times (\text{Scr}/0.9)^{-0.207} \times (\text{Scys}/0.8)^{-0.711} \times 0.995^{\text{age}} (\times 1.08, \text{ if black})$

	> 0.7	≤ 0.8	$130 \times (\text{Scr}/0.9)^{-0.601} \times (\text{Scys}/0.8)^{-0.375} \times 0.995^{\text{age}} (\times 1.08, \text{ if black})$
		> 0.8	$130 \times (\text{Scr}/0.9)^{-0.601} \times (\text{Scys}/0.8)^{-0.711} \times 0.995^{\text{age}} (\times 1.08, \text{ if black})$

Note: Age is shown in years. Scys= serum cystatin, Scr = serum creatinine

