6.2 Phase 2a Objectives

The primary objective of the Phase 2a portion of the study is to evaluate the annualized change in glomerular filtration rate (GFR) in subjects with ADPKD when treated with tesevatinib.

The secondary objectives are to evaluate subjects treated with KD019 with regard to:

- Annualized percent change from baseline in total kidney volume (TKV)
- Annualized change from baseline in the reciprocal of serum creatinine
- Safety profile
- Serum creatinine levels
- PK and tolerability of 2 alternative dosing schedules (dosing on Monday, Wednesday, and Friday of each week and dosing on Monday and Thursday)

In addition, exploratory measures of efficacy will be performed throughout both phases of the study.

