14.3.6 Efficacy/Activity

Descriptive statistics, including confidence intervals for GFR, will be presented over time for the Phase 2a cohort. In addition, identical statistics for the change and percent change from baseline GFR over time will be presented with the 6-month change from baseline being of particular interest.

Similar descriptive statistics will be presented for the reciprocal of serum creatinine endpoints.

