3 STATISTICAL METHODS

3.1 General Methods

3.1.1 Computing Environment

All statistical programming and data analyses will be performed using SAS® Version 9.4 on Windows platform.

3.1.2 Sample Size Justification and power calculations:

Eight subjects per cohort is a standard and reasonable sample size for determination of safety in this Phase 1b portion of the study. Given the frequency and timing of the most common AEs in prior clinical studies of tesevatinib, 8 treated subjects per dose is sufficient to describe the safety profile of tesevatinib in this subject population. These subjects who receive 50 mg daily of tesevatinib will provide 75% likelihood of having at least 1 AE if the true incidence of an AE is 5%.

In the Phase 2a cohort, the 65 subjects in the 50 mg QD dose group will allow an 80% confidence interval of approximately ± 0.64 mL/min about an expected mean 6-month change from baseline of -2.5 mL/min when the standard deviation is 4.0 mL/min.

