3.1.3.1 Continuous variables

Continuous data will be described using descriptive statistics: number of observations (n), mean, standard deviation, median, minimum, and maximum.

Means, medians, standard deviations, and confidence intervals (CIs) will be reported to one decimal place more than the data reported on the case report form (CRF) or by the vendor. Minimum and maximum will be reported to the same number of decimal places displayed on the CRF or by the vendor. P-values will be reported to 4 decimal places.

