3.7.1.2 Serum Creatinine

The annualized percent change from baseline in the reciprocal of serum creatinine will be summarized by cohort using the mITT population. Descriptive statistics will be provided for each cohort [REDACTED]. The change from baseline in the reciprocal of serum creatinine will be calculated using the first and last timepoint for each subject. The annualized percent change from baseline will be calculated as the percent change from baseline divided by total duration in days times 365.25.

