3.7.2 Post-hoc Endpoint Analysis

3.7.2.1 Slope of the change in eGFR

The slope of the change in the estimated GFR was derived from the individual slopes for each patient using the MDRD-4 equation. Descriptive statistics will be provided for each cohort [REDACTED]. The change from baseline in the estimated GFR will be calculated two ways. The first using the first and last timepoint for each subject and the second using all of the available timepoints.

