4 LIST OF TABLES, FIGURES, AND LISTINGS

In all tables, figures and listing, results will be presented by treatment cohorts and overall, unless be otherwise specified.

Table/Listing/Figure	Title
Demographics and Baseline Characteristics	
Tables (14.1.Y.Z)	Table 14.1.1 Screen Failure
	Table 14.1.2 Patient Disposition
	Table 14.1.3 Summary of Demographics and Baseline Characteristics
	Table 14.1.4 Summary of Major Protocol Deviations
	Table 14.1.5 Summary of Medical History
Treatment Exposure and Concomitant Medication	
Tables (14.2.Y.Z)	Table 14.2.1 Summary of Treatment Compliance and Exposure
	Table 14.2.2.a Summary of Prior Medications
	Table 14.2.2.b Summary of Concomitant Medications
Efficacy	
Tables (14.3.Y.Z)	Table 14.3.1 Annualized Change in Estimated Glomerular Filtration Rate
	Table 14.3.2 Annualized Percent Change from Baseline in Height Adjusted Total Kidney Volume
	Table 14.3.3 Annualized Percent Change from Baseline in Reciprocal of Serum Creatinine

	Table 14.3.3.1 Annualized Percent Change from Baseline in Reciprocal of Serum Creatinine for Study 101
Safety	
Tables (14.4.Y.Z)	Table 14.4.1 Summary of AEs
	Table 14.4.1.1 Summary of AEs for Study 101
	[REDACTED]
	Table 14.4.2 Summary of TEAEs
	Table 14.4.2.1 Summary of TEAEs for Study 101
	[REDACTED]
	Table 14.4.3 Summary of TEAEs Related to KD019
	Table 14.4.3.1 Summary of TEAEs Related to KD019 for Study 101
	[REDACTED]
	Table 14.4.4 AEs by Preferred Term and Maximum Severity
	Table 14.4.4.1 AEs by Preferred Term and Maximum Severity for Study 101
	[REDACTED]
	Table 14.4.5 AEs by Preferred Term and Strongest Relationship
	Table 14.4.5.1 AEs by Preferred Term and Strongest Relationship for Study 101
	[REDACTED]
	Table 14.4.6 Summary of Grade ≥ 3 TEAEs by System Organ Class and Preferred Term
	Table 14.4.6.1 Summary of Grade ≥ 3 TEAEs by System Organ Class and Preferred Term for Study 101
	[REDACTED]
	Table 14.4.7 Summary of Grade ≥ 3 TEAEs Related to KD019 by System Organ Class and Preferred Term

	Table 14.4.8 Summary of Serious Adverse Events
	Table 14.4.9 Summary of Serious Adverse Events Related to KD019
	Table 14.4.10 Summary of TEAEs leading to Dose Modification
	Table 14.4.11 Summary of TEAEs Related to KD019 leading to Dose Modification
	Table 14.4.12 Summary of TEAEs leading to Dose Discontinuation
	Table 14.4.13 Summary of TEAEs Related to KD019 leading to Dose Discontinuation
	Table 14.4.14 Summary of Clinical Laboratory: Hematology

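### SAP 3.7 names the Phase 2a primary endpoint as a change in GFR but calculates a percent change, so the primary result cannot be read against the planned precision in mL/min

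*SAP*

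**What the plan says.** Protocol 6.2 gives the Phase 2a primary objective as to "evaluate the annualized change in glomerular filtration rate (GFR) in subjects with ADPKD when treated with tesevatinib". SAP 2.1.1.1 repeats it, and SAP 3.7 names the primary endpoint in the same terms. The formula in SAP 3.7 is then: "The annualized change in GFR will be calculated as the percent change from baseline divided by total duration in days times 365.25". The planned output is "Table 14.3.1 Annualized Change in Estimated Glomerular Filtration Rate"; Figure 14.3.1 has the matching title.

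Protocol 14.3.6 says that "the change and percent change from baseline GFR over time will be presented with the 6-month change from baseline being of particular interest", and it also calls for confidence intervals. The precision statement in Protocol 14.2 and SAP 3.1.2 rests on an "expected mean 6-month change from baseline of -2.5 mL/min when the standard deviation is 4.0 mL/min", with 65 subjects in the 50 mg daily group and an 80% interval of about ±0.64 mL/min.

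On the absolute scale, SAP 3.7.2.1 offers a post-hoc analysis: "The slope of the change in the estimated GFR was derived from the individual slopes for each patient using the MDRD-4 equation".

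For the secondary endpoint on serum creatinine, Protocol 6.2 and SAP 2.1.2.1 state the objective as annualized change in the reciprocal. SAP 3.7.1.2 says: "The annualized percent change from baseline in the reciprocal of serum creatinine will be summarized by cohort using the mITT population".

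**The concern.** The name of the primary endpoint and its formula have different units: mL/min/1.73 m² per year against percent per year. This is hard to read as loose wording, because the documents otherwise keep the two terms apart. In the objectives, percent is attached to TKV only. In the SAP's output list, the eGFR table and figure say change while the TKV table and figure say percent change. Protocol 14.3.6 lists both statistics for GFR.

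Three things follow.

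- Someone programming from the table title and someone programming from the formula would produce different primary tables.
- The result on the SAP's formula cannot be compared with the figures used to justify the sample size, which are absolute, not annualized and for 65 subjects.
- The percent scale depends on each subject's baseline, so a given loss in mL/min has no single equivalent in %/year.

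The post-hoc slope does not fill the gap. It uses MDRD-4 only, names no 6-month estimate or confidence interval, and has no table in SAP Section 4. SAP 3.1.3.1 also lists no interval among its summary statistics: "Continuous data will be described using descriptive statistics: number of observations (n), mean, standard deviation, median, minimum, and maximum". It only sets the decimal places for confidence intervals.

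**Working it through.** **Inputs.** SD 4.0 mL/min, expected 6-month change -2.5 mL/min, n = 65 and 80% interval (Protocol 14.2, SAP 3.1.2). Eligibility limits for eGFR of 35 and 80 mL/min/1.73 m² (Protocol 8.2, criterion 4). Their midpoint, 57.5, is used for illustration only. Six months is taken as 182.625 days, so the annualizing factor is 365.25/182.625 = 2.

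**1. Reproduce the plan's figure.** Half-width = q × SD/√n.

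- Normal quantile: 1.2816 × 4.0/√65 = 0.636 mL/min.
- t quantile, 64 df: 0.642 mL/min.

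Both round to the stated 0.64. A 90% interval would give 0.82 and a 95% interval 0.97. The stated precision is therefore that of an absolute, un-annualized 6-month change.

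**2. Annualize on the absolute scale.** 2 × (-2.5) = -5.0 mL/min per year, with half-width 2 × 0.636 = 1.27 mL/min per year.

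**3. Apply the SAP 3.7 formula to the same change.** Percent per year = 2 × 100 × (-2.5)/baseline. The half-width is 2 × 100 × 0.636/baseline, which holds only if every subject has that same baseline.

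| Baseline eGFR | -2.5 mL/min at 6 months reads as | 0.636 mL/min half-width reads as |
|---|---|---|
| 35 | -14.3%/year | 3.6%/year |
| 57.5 | -8.7%/year | 2.2%/year |
| 80 | -6.25%/year | 1.6%/year |

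The same absolute loss differs by a factor of 80/35 = 2.3 between the two limits. The documents give neither a mean baseline eGFR nor an SD for percent change, so no single planned precision on the percent scale can be derived.

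**4. Precision by cohort.** SAP 3.7 asks for descriptive statistics for each cohort. If the SILK cohort (up to 50) and the earlier Phase 2a 50 mg group (15) are reported separately, the 6-month half-widths are:

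- n = 50: 0.725 (normal) or 0.735 (t) mL/min.
- n = 15: 1.324 (normal) or 1.389 (t) mL/min.

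The ±0.64 is reached only when the two groups are pooled, 15 + 50 = 65.

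**5. Reciprocal of serum creatinine.** Both objectives say change. SAP 3.7.1.2, its formula and Tables 14.3.3 and 14.3.3.1 all say percent change. The SAP's analysis text and titles agree with each other here, so the conflict is with the objectives alone.

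**The case against.** The strongest reply is that absolute GFR change may still be reported. The protocol synopsis mentions estimated GFR within the clinical chemistry item, Table 9-1 includes a laboratory item calculated with the CKD-EPI equations, and SAP 3.8.2 summarizes changes from baseline for all laboratory variables. Listing 16.2.6.1 will show eGFR values, and the SAP does not withdraw the commitment in Protocol 14.3.6. This is fair as far as it goes: the data would be recoverable. But SAP 3.8.2 does not name eGFR. Its tables would be safety-population summaries without a confidence interval, and a listing is not an estimate. None of this supplies the primary analysis in the mITT population.

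Four further points stand in part.

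- The precision statement is un-annualized while the objective is annualized. That gap lies in the protocol itself and would survive a corrected formula, which is why the fix adds a second estimate.
- SAP 3.7 does not define cohort, and SAP Section 4 presents results by treatment cohort and overall. The half-widths for n = 50 and n = 15 are therefore conditional on separate reporting, and 50 is a ceiling.
- The values 35 and 80 are limits for individual subjects, not likely cohort means, so the 2.3-fold spread overstates what a reported mean would show.
- The creatinine item is the weaker one, since the SAP's analysis text is consistent with itself.

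It can also be said that the study is open-label and nonrandomized, with descriptive efficacy, and that the GFR formula sentence closely matches the one for TKV and may simply have been carried over. That may explain the error. It does not settle which unit the primary table should carry.

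**Conclusion.** The plan is wrong as written on this point. SAP 3.7 gives the primary endpoint a name and a formula in different units, and the formula departs from the objective, the table and figure titles and the scale of the precision statement. The planned -2.5 ± 0.64 mL/min at 6 months is arithmetically sound. On the SAP's formula that same change becomes anything from -14.3 to -6.25%/year, depending on baselines between 35 and 80.

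The conclusion about units needs no assumption. The percentages assume the stated baselines and a 6-month interval of 182.625 days. Whether comparisons between cohorts would be distorted is unknown, because baseline eGFR by cohort is not given. SAP 3.7 sets no test or threshold on GFR, so no decision rule is affected. What is affected is the number reported as the Phase 2a primary result, and the unit should be settled before the tables are produced.

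**What to change.** - In SAP 3.7, define the primary endpoint as (GFR at visit - baseline GFR)/days × 365.25, in mL/min/1.73 m² per year.
- Add the un-annualized 6-month absolute change with its 80% confidence interval for the pooled Phase 2a 50 mg daily subjects (15 plus up to 50 in SILK), so that it can be read against -2.5 ± 0.64 mL/min.
- Keep percent change in GFR as a supportive statistic under its own label, as Protocol 14.3.6 plans.
- In SAP 3.7.1.2 and Tables 14.3.3 and 14.3.3.1, use annualized absolute change in the reciprocal of serum creatinine, to match the objective.
- Leave the percent formula for height-adjusted TKV as it is.

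The cost is one formula line in each of two SAP sections, a few table rows, and revised shells and titles. No new data are needed.
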